 - Dose Cohort #1: A minimum of 12 subjects will receive POS IV solution at 3.5 mg/kg (maximum 300 mg/dose, 3.5 mg/kg IV BID on Day 1, then 3.5 mg/kg IV once daily on Days 2-10). Thereafter, subjects will either proceed to POS PFS at 3.5 mg/kg (maximum 300 mg/dose) once daily or continue on POS IV solution, if they are unwilling or unable to tolerate POS PFS.
 - Dose Cohort #2: A minimum of 12 subjects will receive POS IV solution at 4.5 mg/kg (maximum 300 mg/dose, 4.5 mg/kg IV BID on Day 1, then 4.5 mg/kg IV once daily on Days 2-10). Thereafter, subjects will either proceed to POS PFS at 4.5 mg/kg (maximum 300 mg/dose) once daily or continue on POS IV solution if they are unwilling or unable to tolerate POS PFS.
 - Dose Cohort #3: A minimum of 12 subjects will receive POS IV solution at 6 mg/kg (maximum 300 mg/dose, 6 mg/kg IV BID on Day 1, then 6 mg/kg IV once daily on Days 2-10). Thereafter, subjects will either proceed to POS PFS at 6 mg/kg (maximum 300 mg/dose) once daily or continue on POS IV solution if they are unwilling or unable to tolerate POS PFS.

[figure not shown]
*NOTE: In addition to the minimum of 72 subjects required to complete each of the 3 dose cohorts in the 2 age groups, for Dose Cohort #3, an additional 12 subjects will be enrolled

without regard to age group in Dose Cohort #3. Therefore, in total, a minimum of 84 subjects will be enrolled for the entire study.

Specific procedures to be performed during the trial, as well as their prescribed times and associated visit windows, are outlined in the Trial Flow Chart - Section 6.0. Details of each procedure are provided in Section 7.0 – Trial Procedures.

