4.2.2 Rationale for Dose Selection/Regimen

Rationale for dose cohorts 1 and 2 included in original protocol version, MK-5592-097-00

The starting dose of 3.5 mg/kg/day for the POS IV solution and POS PFS formulation was projected via modeling and simulation to achieve the pharmacokinetic (PK) target of an average concentration (C_{avg}) of between 500 and 2500 ng/mL in approximately 90% of patients 2 to 17 years of age (see Section 4.2.3 for details regarding the PK target). In this

study, if at least 10 out of 12 PK-evaluable patients in a dose cohort achieve a C_{avg} in the specified range the PK exposure target will be considered to have been met.

Specifically, utilizing population PK models developed for the POS IV solution and the POS PFS formulation based on observed adult PK data, simulations were conducted to project the exposure in the pediatric population. The PK profile of the POS PFS formulation is expected to be comparable to the POS tablet, based on results of a biocomparison study conducted in adults. The PK concentration versus time profile in the pediatric population was projected by allometrically scaling model parameters by body weight, and simulating the resulting profiles, then calculating the distribution of projected C_{avg} values for each formulation for young children (2 to <7 years) and adolescents (7 to 17 years).

For the POS IV solution, a dose of 3.5 mg/kg/day was expected to result in 91% of young children (2 to <7 years) and 96% of adolescents/older children (7 to 17 years) with C_{avg} values within the target range of 500 and 2500 ng/mL. For the POS PFS formulation, 85% of young children (2 to <7 years) and 90% of adolescents (7 to 17 years) were expected to achieve the PK target.

For the POS IV solution, a dose of 4.5 mg/kg/day was expected to result in 94% of young children (2 to <7 years) and 88% of adolescents/older children (7 to 17 years) with C_{avg} values within the target range of 500 and 2500 ng/mL. For the POS PFS formulation, 90% of young children (2 to <7 years) and 86% of adolescents/older children (7 to 17 years) were expected to achieve the PK target.

Rationale for the addition of third dose cohort (6 mg/kg) in Amendment MK-5592-097-02

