At the time of this amendment, MK-5592-097-02, the 3.5 mg/kg and 4.5 mg/kg dose cohorts have completed enrollment. Based on interim analysis, although the 4.5 mg/kg dose cohort achieved the primary PK target of ~90% of subjects having a steady state C_{avg} POS concentration between 500 and 2500 ng/mL for both the IV solution and oral PFS formulations in both age groups (see [Table 1](#)), the overall exposures (as measured by mean C_{avg} concentrations) were markedly lower than the exposure seen in adult studies of the POS tablet (see [Table 2](#)). Specifically in Age Group 1, mean C_{avg} values were approximately 30-40% lower than what was seen in an adult study of the oral tablet (1080 ng/mL and 976 ng/mL for the IV and PFS, respectively, compared with 1580 ng/mL for the tablet). Therefore, in an effort to achieve systemic POS exposure more closely aligned with the exposure profile in adults, a third dose cohort (6 mg/kg, up to a maximum of 300 mg) is being added to the study.

The selection of the 6 mg/kg/day for Dose Cohort #3 was supported by a modeling and simulation analysis, which predicted the geometric mean C_{avg} and the fraction of subjects with C_{avg} falling within the target range of 500-2500 ng/mL at higher doses for each formulation and age group. Specifically, a population PK model was developed for the IV and PFS formulation based on observed pediatric PK data in Dose Cohorts 1 and 2 (3.5 and 4.5 mg/kg, respectively) and simulations were conducted to project the exposure in the same pediatric age groups for each formulation at doses of 6 and 7.5 mg/kg.

For the POS IV solution, a dose of 6 mg/kg/day is expected to result in 97% of subjects in Age Group 1 (2 to <7 years) and 87% of subjects in Age Group 2 (7 to 17 years) with C_{avg} values within the target range of 500 and 2500 ng/mL. Geometric mean C_{avg} values for IV are predicted to be 1343 ng/mL and 1651 ng/mL for Age Groups 1 and 2, respectively. For the POS PFS formulation, 83.5% of Age Group 1 (2 to <7 years) and 82% of Age Group 2 (7 to 17 years) are expected to achieve the PK target. Geometric mean C_{avg} values for PFS are predicted to be 847 ng/mL and 1083 ng/mL for Age Group 1 and 2, respectively.

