A dose of 7.5 mg/kg/day is predicted to result in less than 80% of Age Group 2 (7 to 17 years) having C_{avg} values within the target range of 500 and 2500 ng/mL for either formulation. This is because a substantial fraction will have C_{avg} values above 2500 ng/mL indicating that this dose would result in too many subjects exceeding the PK target for this Age Group. Taken together, the simulations support that 6 mg/kg/day is the most appropriate dose to be used for both formulations across both age groups in Dose Cohort 3.

The primary PK driver for the addition of the third dose cohort (6 mg/kg, up to a maximum of 300 mg per administration) is the low C_{avg} values seen in Age Group 1 (2 years to <7 years) (see Table 1). Age Group 2 (7 years to 17 years) will be included in Dose Cohort #3 in order to determine if it is possible to identify a single dose for both formulations that achieves adequate exposure across both Age Groups, since a single weight-based dose across all ages is preferable. Because the maximum dose is capped at the adult dose of 300 mg (BID Day 1 and once daily each successive day), the increase in exposure in Age Group 2 will be limited because any subject 50 kg or heavier (most prevalent in the Adolescents/Older Children group) will receive a maximum dose of 300 mg/d.

Table 1 Number of Subjects per Cavg Range by Age group and Formulation for PK Evaluatable Subjects in Dose Cohort #1 (3.5 mg/kg/d) and Dose Cohort #2 (4.5 mg/kg/d) of MK-5592-097

Dose	Age Group	Dose Type	N	<200	200 - <500	500 - <2500	2500 - <3650	>3650
3.5 mg/kg	1 (2 to <7 yrs old)	IV	11	0	2 (18%)	9 (82%)	0	0
		PFS	5 [†]	0	3 (60%)	2 (40%)	0	0
	2 (7 to 17 yrs old)	IV	19 [†]	0	0	18 (95%)	1 (5%)	0
		PFS	10	0	1 (10%)	9 (90%)	0	0
4.5 mg/kg	1 (2 to <7 yrs old)	IV	13	0	0	13 (100 %)	0	0
		PFS	7 [†]	0	1 (14%)	6 (86%)	0	0
	2 (7 to 17 yrs old)	IV	14	0	0	13 (93%)	1 (7%)	0
		PFS	8 [†]	0	0	8 (100%)	0	0

[†]Due to subjects being at steady state, the predose value was assumed to be equal to C24hr for the 2 subjects (for 3.5 mpk PFS), 1 subject (for 3.5 mpk IV) and 2 subjects (for 4.5 mpk PFS) missing the 24 hour PK sample and this value was used to replace the missing C24hr in order to calculate Cavg.

Table 2 Summary of Posaconazole Plasma Steady State Pharmacokinetic Parameters for Dose Cohort #1 (3.5 mg/kg/d) and Dose Cohort #2 (4.5 mg/kg/d) by Age Group and Dose Formulation in PK Evaluable Subjects from MK-5592-097

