8.2.5 Power and Sample Size

The sample size is not based on any formal power calculation.

The total sample size for the study is a minimum of 84 subjects (72 PK-evaluable subjects) distributed across the 3 dose cohorts as follows:

Dose cohort #1 (a minimum of 24 PK evaluable subjects, divided 12 per Age Group).

Dose cohort #2 (a minimum of 24 PK evaluable subjects, divided 12 per Age Group).

Dose cohort #3 (a minimum of 36 subjects, divided as 12 PK evaluable subjects per Age Group and an additional 12 distributed across either Age Group).

The actual total number of enrolled subjects may be greater than 84 in order to ensure a minimum of 72 subjects that meet PK evaluability criteria.

At the time of this amendment (MK-5592-097-02), enrollment in Dose Cohorts #1 and #2 is complete. Therefore, the remaining target enrollment for this amendment is a minimum 36 subjects in Dose Cohort #3 (12 PK evaluable subjects per age group and an additional 12 distributed across either age group).

If successful dose selection is defined as at least 10 out of 12 (82.2%) patients per age/dose group achieving a $C_{avg} > 500$ ng/mL, the chance of achieving success is at least 89%, based on a sample size of 12 patients in each age/dose cohort using a binomial distribution ($n=12$, $p=0.90$), where p = probability of success.

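### Section 8.2.5 gives 12 evaluable subjects per cell and an 89% chance without naming a formulation; neither is assured for PFS, and the plan's own predictions do not support 89% for PFS in Age Group 1

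*Combined protocol and SAP*

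**What the plan says.** Section 8.2.5 disclaims a formal power calculation. It then defines successful dose selection as at least 10 of 12 subjects per age/dose group with C_avg above 500 ng/mL, and says "the chance of achieving success is at least 89%, based on a sample size of 12 patients in each age/dose cohort", using a binomial with p = 0.90. Section 8.1.4 likewise asks for 72 PK-evaluable subjects. Neither section says whether evaluable means IV, PFS or both.

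Other sections bear on this:

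- Section 2.1 has each formulation assessed separately within a dose cohort, and Section 4.2.4.3 makes C_avg primary for both.
- Sections 8.1.1 and 8.2.1 define the evaluable set by at least 7 days of IV and full sampling on IV. Section 5.9 replaces a subject only for not completing 7 days of IV. Section 2.1 lets subjects finish on IV alone.
- Section 4.2.2 states the 10-of-12 rule on a different criterion: the target is met "if at least 10 out of 12 PK-evaluable patients in a dose cohort achieve" a C_avg within 500–2500 ng/mL.
- For 6 mg/kg, Section 4.2.2 predicts the in-range share: "For the POS PFS formulation, 83.5% of Age Group 1 (2 to <7 years) and 82% of Age Group 2 (7 to 17 years". Geometric mean C_avg "values for PFS are predicted to be 847 ng/mL and 1083 ng/mL for Age Group 1 and 2, respectively".
- On the extra subjects, Section 2.1 says "for Dose Cohort #3, an additional 12 subjects will be enrolled", without regard to age group.

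**The concern.** The 10-of-12 statement is the only quantitative support for 12 subjects per cell, and as written it reads as covering both formulations. The interim review did apply the target to PFS: Section 4.2.2 says "although the 4.5 mg/kg dose cohort achieved the primary PK target of ~90% of subjects" for both formulations, on PFS cells of 7 and 8 subjects.

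A reader would therefore expect 12 evaluable PFS subjects per age group in Dose Cohort #3 and an 89% chance of meeting the rule. The design does not assure that number, and the same amendment predicts PFS shares below 0.90. Age Group 1 matters most, because its low C_avg is given as "The primary PK driver for the addition of the third dose cohort". Only Dose Cohort #3 is open to correction in advance, since the first two cohorts are fully enrolled.

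**Working it through.** **1. Reproduce the stated figure.** With n = 12, P(X ≥ 10) = 66·p^10·(1−p)^2 + 12·p^11·(1−p) + p^12. At p = 0.90 this is 0.2301 + 0.3766 + 0.2824 = 0.889, so the 89% is correct for its inputs. (10/12 is 83.3%, not the printed 82.2%.)

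**2. The number of subjects.** Table 1 of Section 4.2.2 ("Number of Subjects per Cavg Range by Age group and Formulation for PK Evaluatable Subjects") gives these interim counts:

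| Dose | Age Group | IV | PFS |
|---|---|---|---|
| 3.5 mg/kg | 1 | 11 | 5 |
| 3.5 mg/kg | 2 | 19 | 10 |
| 4.5 mg/kg | 1 | 13 | 7 |
| 4.5 mg/kg | 2 | 14 | 8 |

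Totals are PFS 30 and IV 57, a ratio of 30/57 = 53%. No PFS cell reached 12.

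**3. The in-range form (500–2500 ng/mL) at n = 12**, with p taken directly from the 6 mg/kg predictions in Section 4.2.2:

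| Cell | p | P(X ≥ 10) |
|---|---|---|
| PFS, Age Group 1 | 0.835 | 0.683 |
| PFS, Age Group 2 | 0.82 | 0.630 |
| IV, Age Group 1 | 0.97 | 0.995 |
| IV, Age Group 2 | 0.87 | 0.802 |

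**4. The above-500 form at n = 12.** The documents give no predicted share above 500 ng/mL, so an assumption is needed. I take C_avg as lognormal with the stated geometric mean (GM) and solve for σ in: in-range share = Φ(ln(2500/GM)/σ) − Φ(ln(500/GM)/σ).

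- PFS, Age Group 1: GM 847 and share 0.835 give σ = 0.506. P(>500) = Φ(0.527/0.506) = 0.851, with 1.6% above 2500. Then P(X ≥ 10) = 0.740.
- PFS, Age Group 2: GM 1083 and share 0.82 give σ = 0.599. P(>500) = Φ(0.773/0.599) = 0.901, with 8.1% above 2500. Then P(X ≥ 10) = 0.893.
- IV: the same method with GM 1343 and 1651 gives P(>500) of 0.999 in both age groups, so P(X ≥ 10) is near 1.

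**5. How far step 4 depends on the lognormal.** P(>500) equals the in-range share plus the share above 2500. Without any distribution it lies between 0.835 and 1 in Age Group 1, and between 0.82 and 1 in Age Group 2. To reach p = 0.90, Age Group 1 would need 0.90 − 0.835 = 6.5% of subjects above 2500 ng/mL, about four times the fitted 1.6%. Age Group 2 would need 0.90 − 0.82 = 8.0%, about what the fit gives.

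**The case against.** The strongest reply is that the 89% and the in-range shares concern different criteria. Section 4.2.3 makes exceeding 500 ng/mL the primary goal, so the above-500 rule in 8.2.5 is not a slip. On that rule Age Group 2 PFS gives about 0.89, which agrees with the plan. This stands, and it limits the conclusion for Age Group 2 to the in-range form.

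It is also fair that this is an estimation study with descriptive summaries, that the lower PFS predictions are disclosed in Section 4.2.2, and that Dose Cohort #3 is the last cohort with no formal interim analysis. No escalation decision hangs on the figure. That reduces the consequence but does not settle what the 89% refers to.

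Three stronger readings are tempting, and the documents do not support them:

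- **That smaller PFS numbers push the chance well below these values, to around one half.** This needs the 10-of-12 rule extended to other n, which the plan never does, and the answer then turns on rounding. At p = 0.90, requiring 9 of 10 gives 0.736 but 8 of 10 gives 0.930; 10 of 11 gives 0.697 but 9 of 11 gives 0.910; 5 of 6 gives 0.886, almost the same as 10 of 12.
- **That the final PFS count will match the interim ratio.** The final PFS analysis is population PK and uses sparse outpatient samples, so the count may be higher by a number the documents do not give. The 12 extra subjects may add to it as well.
- **That 12 and 89% are secure for IV.** One completed IV cell has 11. Replacement depends only on 7 days of IV, while evaluability also needs full sampling. On the in-range form, Age Group 2 IV gives 0.80.

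**Conclusion.** The point holds as one of scope. The arithmetic in 8.2.5 is correct, but the target of 12 rests on IV evaluability and is not assured for PFS. The stated chance of at least 89% compares with 0.68 (in range) and about 0.74 (above 500) for Age Group 1 PFS, so it is unsupported there on either form. For Age Group 2 PFS it is unsupported in range (0.63) and supported above 500 (about 0.89), provided n reaches 12.

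The in-range values need only the plan's predicted shares and independent subjects. The above-500 values also need the lognormal assumption. The correction is worth making before Dose Cohort #3 reports, because Age Group 1 exposure is the reason that cohort was added.

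**What to change.** 1. In 8.1.4 and 8.2.5, state that the target of 12 per age/dose group is defined by IV evaluability and is not assured for PFS.
2. In 8.2.5, name one criterion (above 500, or 500–2500 ng/mL) and restate the Dose Cohort #3 probability by formulation and age group at n = 12 from the plan's predicted proportions. For Age Groups 1 and 2 in turn, the in-range values are IV 0.995 and 0.80, PFS 0.68 and 0.63. The above-500 values are PFS about 0.74 and 0.89 and IV near 1, with the lognormal assumption stated.
3. Report the PFS proportion already planned in 8.2.1 with its actual n and an exact 95% CI. At 10 of 12, for example, the interval is 52% to 98%.

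Do not add a rule scaled to the actual PFS n; that would be a new criterion, with a threshold that jumps with rounding.

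The cost is some wording and one interval per reported proportion, with no added subjects, visits or samples. The downside is a less favourable stated probability for PFS.

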There will be two age groups in this study. Both age groups will enroll simultaneously. The original protocol, MK-5592-097-00, outlined the study of two dose cohorts, 3.5 mg/kg and 4.5 mg/kg. At the time of this amendment, these dose cohorts, 3.5 mg/kg and 4.5 mg/kg, have completed enrollment. This protocol amendment, MK-5592-097-02, adds a third dose cohort, 6 mg/kg, based on the observed PK in Dose Cohort 1 and 2. See the Study Rationale in Section 4.2.2. Dose cohorts will enroll sequentially. Each POS formulation (IV and POS PFS) will be assessed separately within each dose cohort. If a dose cohort within a specific age group has an acceptable safety profile and does not achieve the target exposure for both formulations, dosing will be escalated to the next dose cohort within that same age group.

The two age groups (Young Children [ages 2 - < 7 years; Age Group 1]; Adolescents/Older children [7 to 17 years; Age Group 2]) will enroll simultaneously:

- **Age Group 1: Young Children (minimum of 36* subjects, age 2 to <7 years)**
 - Dose Cohort #1: A minimum of 12 subjects will receive POS IV solution at 3.5 mg/kg (maximum 300 mg/dose, 3.5 mg/kg IV BID on Day 1, then 3.5 mg/kg IV once daily on Days 2-10). Thereafter, subjects will either proceed to POS PFS at 3.5 mg/kg (maximum 300 mg/dose) once daily or continue on POS IV solution, if they are unwilling or unable to tolerate POS PFS.
 - Dose Cohort #2: A minimum of 12 subjects will receive POS IV solution at 4.5 mg/kg (maximum 300 mg/dose, 4.5 mg/kg IV BID on Day 1, then 4.5 mg/kg IV once daily on Days 2-10). Thereafter, subjects will either proceed to POS PFS at 4.5 mg/kg (maximum 300 mg/dose) once daily or continue on POS IV solution, if they are unwilling or unable to tolerate POS PFS.
 - Dose Cohort #3: A minimum of 12 subjects will receive POS IV solution at 6 mg/kg (maximum 300 mg/dose, 6 mg/kg IV BID on Day 1, then 6 mg/kg IV once daily on Days 2-10). Thereafter, subjects will either proceed to POS PFS at 6 mg/kg (maximum 300 mg/dose) once daily or continue on POS IV solution, if they are unwilling or unable to tolerate POS PFS.
- **Age Group 2: Adolescents/Older Children) (minimum of 36* subjects, age 7 to 17 years)**

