5.2 Trial Treatment(s)

POS study drug will be administered to patients with neutropenia associated with chemotherapy given for a diagnosis of acute leukemia (newly diagnosed or relapsed), myelodysplasia, severe aplastic anemia, high risk neuroblastoma, advanced NHL, or hemophagocytic lymphohistiocytosis. In addition, recipients of an autologous HSCT or recipients of autologous HSCT during the pre-engraftment (neutropenic) period are eligible.

The subject population will be divided into 2 age groups. Age Group 1 will be Young Children, who are aged 2 years to <7 years of age, and Age Group 2 will be Adolescents/Older Children, who are aged 7 to 17 years of age.

The two formulations will be studied in all subjects in a sequential manner (POS IV solution, followed by POS PFS formulation). There will be three pre-specified dosage cohorts in this study. The decision to move to the next higher dose cohort may be done independent of complete enrollment of the other age group.

The first dosage cohort (Dose Cohort #1) will receive 3.5 mg/kg (up to a maximum of 300 mg) BID of POS IV solution on Day 1, followed by 3.5 mg/kg/day (up to a maximum of 300 mg) of POS IV solution administered once daily from Day 2 through Day 10; thereafter, treatment with the POS PFS formulation at a dose of 3.5 mg/kg/day will be initiated and administered for at least 10 additional days. Subjects who are unwilling or unable to tolerate a transition to oral therapy after Day 10 may continue on POS IV solution at the discretion of the investigator. Subjects who continue on POS IV solution beyond Day 10 may (a) transition to POS PFS at any time up through Day 18 that they are able to tolerate oral medication, or (b) complete study treatment with POS IV solution only. POS PFS may also be continued beyond 10 days of treatment if the subject remains neutropenic. The total maximum duration of POS, administered as either IV solution or PFS, is 28 days. Preliminary PK data for each formulation will be reviewed upon completion of the first dosage cohort. If the PK exposure target is achieved in an age group in Dose Cohort #1, and an appropriate pediatric dose can be determined for both formulations, then the second dosage cohort may not be enrolled for that age group.

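### The 89% chance of successful dose selection in Section 8.2.5 covers one formulation in one age group; for the units on which the plan judges a dose it is a ceiling, not a floor

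*Combined protocol and SAP*

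**What the plan says.** Section 8.2.5 opens with the statement that "The sample size is not based on any formal power calculation". It then defines successful dose selection as "at least 10 out of 12 (82.2%) patients per age/dose group achieving a" value above 500 ng/mL for C_avg. For this it states that "the chance of achieving success is at least 89%, based on a sample size of 12 patients in each age/dose cohort". The calculation behind that figure is a binomial with 12 patients and a per-patient success probability of 0.90. Formulation is not mentioned, and no joint probability is given there or elsewhere in the SAP.

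Other sections judge a dose on more than one set of 12 results:

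- Section 2.1: "Each POS formulation (IV and POS PFS) will be assessed separately within each dose cohort". If an age group has acceptable safety and "does not achieve the target exposure for both formulations, dosing will be escalated to the next dose cohort within that same age group".
- Section 5.2: Dose Cohort #2 may be omitted for an age group only if Dose Cohort #1 met the exposure target and a dose can be determined for both formulations. The same section says: "The two formulations will be studied in all subjects in a sequential manner".
- Section 4.2.2: older children are included in Dose Cohort #3 to find out whether it is possible to "identify a single dose for both formulations that achieves adequate exposure across both Age Groups".

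**The concern.** Each subject can contribute two C_avg values, one on IV and one on PFS. A binomial with n = 12 handles one value per subject, so it describes one formulation in one age group. Section 8.2.5 nevertheless attaches the result to successful dose selection as a whole and calls it a minimum.

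The figure is the only operating characteristic in the SAP, and it follows directly after the enrolment target for Dose Cohort #3. A reader may well attach it to that cohort's aim. If one of the four cells then misses 10 of 12, the miss could be taken as evidence against a single dose. At the plan's own p and n, a miss in at least one cell has a probability of about 21% to 38% by chance alone.

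**Working it through.** **Inputs.** n = 12, p = 0.90 and the 10-of-12 threshold come from Section 8.2.5. Two formulations and two age groups come from Sections 2.1 and 4.2.2. The age groups are different children, so their probabilities multiply. IV and PFS are given to the same children, so their dependence is unknown and is bracketed.

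**1. The plan's own figure.** P(X ≥ 10 | 12, 0.90) = 0.2301 + 0.3766 + 0.2824 = 0.8891. This matches 89% after rounding.

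**2. Both formulations within one age group.**
- Independent: 0.8891² = 0.791.
- Fully dependent: 0.889. No form of dependence can exceed this.

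**3. All four cells.**
- Independent: 0.8891⁴ = 0.625.
- Fully dependent within each age group: 0.8891² = 0.791. No IV/PFS dependence can exceed this.
- A simulation with correlated normal variables behind the pass/fail results gives about 64%, 65%, 66% and 70% at within-subject correlations of 0.3, 0.5, 0.7 and 0.9. The upper end of the range therefore needs nearly perfect agreement.
- Chance of at least one miss: 1 − 0.791 = 21% to 1 − 0.625 = 38%.

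**4. Sensitivity to p** (four cells, independent to fully dependent, same p in every cell):

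| p | One cell | Four cells |
|---|---|---|
| 0.85 | 0.736 | 0.29 to 0.54 |
| 0.90 | 0.889 | 0.62 to 0.79 |
| 0.95 | 0.980 | 0.92 to 0.96 |

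**5. Sensitivity to n.** Section 8.2.5 adds 12 subjects to Dose Cohort #3 without giving a success rule for them. Suppose they split evenly and the rule becomes at least 15 of 18 (83.3%, the same proportion as 10 of 12). One cell is then 0.902, and four cells are 0.661 to 0.813.

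The PFS cells could instead be smaller than 12. Sections 8.1.1 and 8.2.1 define the primary PK population by IV treatment and IV sampling, and the PFS cells in Table 1 held 5, 10, 7 and 8 subjects. If the threshold is kept at 83.3% or more (an assumption), one PFS cell at p = 0.90 passes with probability 0.590 (5 of 5), 0.850 (6 of 7), 0.813 (7 of 8) or 0.736 (9 of 10).

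**6. The plan's own projections at 6 mg/kg.** Section 4.2.2 projects the share of subjects within 500-2500 ng/mL as 97% and 87% (IV, Age Groups 1 and 2) and 83.5% and 82% (PFS). It also gives projected geometric means of 1343, 1651, 847 and 1083 ng/mL. The two success rules need separate calculations.

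- *Section 4.2.2 rule (10 of 12 within 500-2500).* The cells are 0.995, 0.802, 0.683 and 0.630. Their product is 0.34. With full dependence within age group the bound is 0.683 × 0.630 = 0.43.
- *Section 8.2.5 rule (10 of 12 above 500).* The documents do not give the share above 500. Assume C_avg is log-normal and solve for the log-scale SD σ in Φ(ln(2500/GM)/σ) − Φ(ln(500/GM)/σ) = projected share. This gives σ of about 0.33, 0.37, 0.51 and 0.60, and P(C_avg > 500) of about 0.999, 0.999, 0.85 and 0.90. The cells are then about 1.00, 1.00, 0.74 and 0.89. The joint chance is 0.74 × 0.89 ≈ 0.66 whichever IV/PFS dependence is assumed, because the IV cells pass almost surely.

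**The case against.** The sentence limits itself to an age/dose group of 12 and is correct for what it computes, so there is no arithmetic error in it. The sample size is expressly not built on a power calculation, the primary objective is estimation, and the PK analysis is descriptive. No enrolment target or analysis would change if a joint figure were printed.

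A reader might infer that Dose Cohort #3 must pass in four cells and has only a 62% to 79% chance of doing so. The documents do not support that reading. Section 4.2.2 asks whether a single dose can be found, calls a single dose preferable, and does not tie adequate exposure there to 10 of 12. The escalation rule in Section 2.1 works within one age group, and Dose Cohort #3 is the final cohort (Section 4.2.2.2). Section 4.2.2 also reports that 4.5 mg/kg met the target for both formulations in both age groups, yet a further cohort was added because mean exposure was low. Passing cells was therefore not the whole decision.

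A reader might also quote 0.34 to 0.43 as the plan's true chance of success. That sets projections for 500-2500 ng/mL against a rule that counts only values above 500, and so scores subjects above 2500 as failures when Section 8.2.5 passes them.

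All of this stands and limits the point. It does not remove the mismatch: Section 8.2.5 calls a one-formulation figure the chance of successful dose selection and a minimum, while Sections 2.1 and 5.2 require both formulations within an age group.

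**Conclusion.** The point holds as one of scope. The 89% is right for one formulation in one age group. At p = 0.90 and n = 12, it is the most that can be claimed for both formulations within an age group (79% to 89%), and it lies above anything attainable for all four cells (62% to 79%). The lower ends assume that IV and PFS are independent; the upper ends hold under any dependence. The four-cell range measures how demanding the aim in Section 4.2.2 is and is not the chance of meeting a written criterion.

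The words *at least* can be defended for a single cell if p is 0.90 or more, but not for a dose judged on both formulations at p = 0.90. The result is sensitive to p: at 0.95 in every cell, even the four-cell chance exceeds 89%. Under the log-normal assumption, the plan's own projections at 6 mg/kg give about 0.74 for PFS in Age Group 1 and about 0.66 jointly on the rule of C_avg above 500, so they do not support 89% as a minimum either.

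Nothing here shows that the sample size is inadequate or that the dose should differ.

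**What to change.** Replace the last sentence of Section 8.2.5 with wording such as: *If p = 0.90 and n = 12, the chance of meeting the criterion is about 89% per age group and formulation; 79% to 89% for both formulations within an age group; and about 62% to 79% for all four cells of Dose Cohort #3. The ranges run from independent to fully dependent IV and PFS results. The four-cell figure describes the aim in Section 4.2.2 and is not a pass criterion.* Drop *at least*.

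Add that the figures assume 12 evaluable subjects in each PFS cell, which the IV-based evaluability definition does not ensure, and say how the additional 12 subjects enter the criterion.

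If a figure based on the Section 4.2.2 projections is added, match it to its rule: 0.34 to 0.43 for 500-2500 ng/mL, or about 0.66 for C_avg above 500 with the log-normal assumption stated. In the same edit, correct the printed 82.2% (10/12 = 83.3%) and reconcile the two success rules in Sections 4.2.2 and 8.2.5.

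The cost is a few sentences of SAP text and a less favourable stated probability. No subjects, procedures or analyses are added.
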